6.4.3. Analysis of Immune Responses

The primary immunogenicity time points are 2 and/or 4 weeks after the first dose, although immunogenicity data at other time points will be examined as well. The magnitude of the

responses will be compared within subjects (before and after first dose; before and after second dose) and between subjects (between dose cohorts and between those who receive Alum and those who do not). The primary comparisons at 2 and/or 4 weeks post first dose will be compared using Wilcoxon Rank Sum tests, but regression models will also be explored that model post-dose immune response as a function of pre-dose immune response, dose, Alum (yes/no), and possibly demographic variables such as age and gender. Immunogenicity will be analyzed for a variety of cohorts defined based on vaccination status, and specified in the Statistical Analysis Plan (SAP). At minimum these may include ITT, PP, and mITT cohorts.

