4.2.3. Product Administration

On each injection day (prior to injection), laboratory and research samples will be collected and subjects will be clinically evaluated. A subject who arrives at the clinic with fever or evidence of an acute illness, which precludes administration of the vaccine, may be rescheduled within the allowed visit window. Pregnancy test results for females of reproductive potential must be confirmed as negative within 24 hours before each injection.

When choosing a site for injection, clinicians should consider whether there is an arm injury, local skin problem or significant tattoo that precludes administering the injection or will interfere with evaluating the arm after injection. It is recommended, but not required, that the first injection be administered into the non-dominant arm. It is preferred, but not required, to alternate arms for study injections.

All injections will be administered IM into upper arm deltoid muscle by needle and syringe. For groups receiving adjuvant, the adjuvant will be field mixed by the site pharmacist prior to administration.

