4.3. Dose Continuation and Dose Escalation Plans

Dose groups will be enrolled sequentially, with no more than one subject per day for the first 2 study injections of the study. Dose continuation and escalation will occur after subjects have completed the first injection and following interim safety data reviews. Approval to proceed will be obtained from the Protocol Safety Review Team (PSRT).

- The dose continuation review (for 50 mcg) will occur when at least 5 subjects who received 50 mcg in either Group 1 or Group 2 have completed post-injection follow-up through completion of the 7 day diary card. If assessed as safe to continue, enrollment of additional subjects in Group 1 and Group 2 may proceed.
- The first dose escalation review (50 mcg to 150 mcg) will occur when at least 10 subjects who received 50 mcg in either Group 1 or Group 2 have completed post-injection follow-up through at least the "Study Week 2" visit. If assessed as safe, enrollment of additional subjects may proceed until at least 10 subjects have enrolled in each Group 1 and Group 2. After that, enrollments may begin in Group 3 and Group 4.
- The second dose escalation review (150 mcg to 500 mcg) will occur when at least 10 subjects who received 150 mcg in either Group 3 or Group 4 have completed post injection follow-up through at least the "Study Week 2" visit. If assessed as safe, enrollment of additional subjects may proceed until at least 10 subjects have enrolled in each Group 3 and Group 4. After that enrollments may begin in Group 5 and Group 6.

- The final dose continuation review (for 500 mcg) will occur when at least 10 subjects who received 500 mcg in either Group 5 or Group 6 have completed post injection follow-up through at least the “Study Week 2” visit. If assessed as safe, enrollment of additional subjects may proceed until at least 10 subjects have enrolled in each Group 5 and Group 6.
- The second injection for all groups may occur once the first dose of that dose level has been assessed as safe at the “Study Week 2” visit.

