6.3. Sample Size and Accrual

The study design is to have 90 healthy adult subjects divided equally among 6 groups.

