6.4.6. Randomization of Treatment Assignments

At the start of the study, subjects will be randomized 1:1 to Groups 1 and 2. If the criteria for the first Dose Escalation are met, procedures for the interim safety review are completed, and there are at least 10 people enrolled in each of Groups 1 and 2, subjects will be randomized 1:1 in Groups 3 and 4. If the criteria for the second Dose Escalation are met, procedures for the interim safety review are completed, and there are at least 10 people enrolled in each of Groups 3 and 4, subjects will be randomized 1:1 in Groups 5 and 6. Once all groups have at least 10 subjects per group, or if the dose escalation criteria are not met, subjects will be randomized in equal proportions to all groups that are open.

The subject and the study clinicians will be informed of the subject's group assignment upon completing the enrollment in the database.

To decrease the potential for participant dropouts during the period between randomization and initial vaccination, randomization will occur on Day 0 after the study consent is signed and eligibility is confirmed. If subjects accrued to a study group do not complete the number of injections and/or a follow-up duration specified, then additional subjects may be accrued in that group.

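### At most 5 of the planned 15 per group are randomised between doses, yet unadjusted rank-sum tests are primary for dose and alum contrasts alike and the baseline-adjusted model is only explored

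*Combined protocol and SAP*

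**What the plan says.** **Allocation.** Section 4.3 states: "Dose groups will be enrolled sequentially". Section 6.4.6 starts with 1:1 randomisation to Groups 1 and 2. It then opens 150 mcg on the condition that "there are at least 10 people enrolled in each of Groups 1 and 2, subjects will be randomized 1:1 in Groups 3 and 4", and uses the same rule for 500 mcg. Allocation in equal proportions to all open groups starts later: "Once all groups have at least 10 subjects per group". Section 6.3 plans 90 subjects "divided equally among 6 groups".

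**Analysis.** Section 6.4.3 lists the comparisons "between subjects (between dose cohorts and between those who receive Alum and those who do not" in one sentence and does not separate them by how subjects were allocated. On the method for the main early time points it says: "post first dose will be compared using Wilcoxon Rank Sum tests, but regression models will also be explored". The model named there regresses post-dose response on pre-dose response, dose and alum, and possibly demographics. The section does not say whether the rank-sum test is applied to post-dose titre or to fold-rise. Analysis cohorts are left to be "specified in the Statistical Analysis Plan (SAP", and that separate SAP is not part of the text supplied.

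**Baseline sample.** Section 4.2.3 provides the pre-dose measurement: "On each injection day (prior to injection), laboratory and research samples will be collected".

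**The concern.** An alum contrast within a dose compares subjects randomised against each other over the same period. A whole-cohort dose contrast mostly compares subjects enrolled in different periods. Section 6.4.6 makes this visible, but Section 6.4.3 does not carry it into the analysis. Both kinds of contrast get the same unadjusted test, and the one named method that uses the pre-dose titre is secondary.

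Two things are at stake. The first is precision: a baseline that is collected anyway is not used in the main comparison, for dose or for alum. The second is robustness: if pre-dose titre differed between enrolment periods, an unadjusted dose contrast would take in part of that difference. The dose contrast is meant to be used, since Section 6.3.2 presents power between two dose cohorts. The stakes are limited all the same. Immunogenicity is secondary, Section 3.2 asks for the response in each group, and no dose-superiority hypothesis is stated.

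**Working it through.** **1. How many are randomised between doses.** Planned per group: 90 / 6 = 15. Minimum enrolled in each group before cross-dose allocation opens: 10. So at most 15 − 10 = 5 per group, or 6 × 5 = 30 of 90 (33%). It is a maximum because the threshold is at least 10. Section 1.3 reports 95 enrolled and all escalation steps completed, so at most 95 − 60 = 35 in total; the split by group is not given.

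**2. The plan's own power figure.** Section 6.3.2 gives 90% or better for 0.45 log10 with 15 per group, and about 0.3 log10 with 30, at SD 0.5. Alpha is not stated; two-sided 0.05 is assumed.
- As a paired comparison with SD of change 0.5: 0.45 / (0.5/√15) = 3.49, power 89.9%; 0.30 / (0.5/√30) = 3.29, power 88.8%. This reproduces the figure.
- As two independent groups: 0.45 / (0.5·√(2/15)) = 2.46, power 66%; 0.30 / (0.5·√(2/30)) = 2.32, power 63%.

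The stated power is therefore that of the within-subject comparison. Between-group contrasts have less, so a gain in precision is useful there.

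**3. Gain with no drift** (15 v 15, 0.45 log10, SD 0.5 before and after dosing; the pre-post correlation r is assumed because the documents give none).
- Residual SD after adjustment is 0.5·√(1 − r²) = 0.477, 0.433 and 0.357 at r = 0.3, 0.5 and 0.7. The two-sample t approximation gives 70, 78 and 91%.
- Simulation of the named methods gives 62–63% for rank-sum on post-dose titre, against about 69, 77 and 90% adjusted.
- If fold-rise were the tested variable, its SD is 0.5·√(2 − 2r) = 0.592, 0.500 and 0.387, and the two-sample t power is 52, 66 and 87%. The adjusted model still does better, but by little at r = 0.7.

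**4. If pre-dose titre drifted** (assumed). Let the periods in which each dose was enrolled alone differ by D in mean pre-dose log10 titre, and let a fraction c of that shift carry through to the post-dose titre. The non-concurrent share is 10/15 = 2/3. The biases are:
- post-dose titre: (2/3)·c·D
- fold-rise: −(2/3)·(1 − c)·D
- adjusted model: about (2/3)·(c − slope)·D

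At c = 1 and D = 0.1, 0.2 or 0.3, the first is 0.07, 0.13 or 0.20 log10. Simulated size at nominal 5%, with D = 0.3, r = 0.5 and 30 v 30 (alum pooled, 20 + 10 per dose), ranging over the position of the final stage:

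| Carry-through | Rank-sum, post-dose titre | Rank-sum, fold-rise | Adjusted |
|---|---|---|---|
| full | 25–31% | 5% | 10–14% |
| half | 10–12% | 10–11% | 5% |
| none | 5% | 25–30% | 10–13% |

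At 15 v 15, rank-sum on post-dose titre has size 12–16% (full), 7–8% (half) and 5% (none). Which variable is tested decides the direction of any bias, so it needs to be named. The adjusted model has the lowest worst case here, and also at r = 0.3 (at most 19%, against 30% for post-dose titre and 23% for fold-rise). At r = 0.7 its worst case, 30%, is level with post-dose titre at 31%; fold-rise reaches 47%.

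**The case against.** The other side has real force. Sequential enrolment is inherent in dose escalation, the allocation rule is fully disclosed, and no section claims that dose was randomised throughout. The documents give no drift: the Introduction says only that RSV infection recurs through life. All the drift figures above are therefore hypothetical. At 15 v 15 with half carry-through, the size of rank-sum on post-dose titre is only 5, 5–6 and 7–8% at D = 0.1, 0.2 and 0.3.

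Adjustment can also do harm. If drift did not carry through, then at D = 0.3 and 30 v 30 the adjusted model's size would be 7, 10–13 and 19–30% at r = 0.3, 0.5 and 0.7, against 5% for rank-sum on post-dose titre. The more than 10-fold boost in Section 1.3 may dilute carry-through. It would probably also lower the pre-post slope, and the model's bias depends on the gap between the two; but a low correlation also shrinks the precision gain towards the 69% case. Finally, results have been seen, and moving the main estimate of an open-label trial at this stage invites a charge of post hoc selection.

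This removes any claim that the dose results are biased. It leaves the count, the unequal standing of the two contrasts, the unnamed test variable and the precision gain, which needs no drift. The separate SAP may settle some of this; Section 6.4.3 cites it only for analysis cohorts.

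**Conclusion.** The point holds as a low-cost improvement, not as a flaw that invalidates a result. At most 30 of the planned 90 subjects are randomised between doses, and this follows from the text alone. The main benefit of adjustment is power: about 63% rising to about 69, 77 or 90% for 0.45 log10 at 15 v 15, given SD 0.5 and an assumed correlation of 0.3, 0.5 or 0.7. Protection against drift is partial and conditional on assumptions.

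Three stronger readings are not supported.
- A reader might infer that the dose comparisons are biased, or that their error rate is 25–31%. That needs a drift of 0.3 log10, full carry-through and pooled alum arms, and none of these is in the documents.
- A reader might take 60/95 = 63% as a floor for the non-concurrent share at 95 enrolled. It is not: if all five extra subjects fell in one dose, that dose's share would be 20/35 = 57%.
- A reader might ask for a concurrent-only dose analysis as a required output. Its 95% interval half-width is 0.47 log10 at 10 v 10 and 0.73 at 5 v 5, so it could neither confirm nor exclude a bias of 0.07–0.20.

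**What to change.** In Section 6.4.3:

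1. Make the model named there (log10 post-dose on log10 pre-dose, dose and alum) the main estimate for between-group contrasts, with a confidence interval.
2. Report the named rank-sum test beside it, and state whether it is applied to post-dose titre or to fold-rise.
3. State that whole-cohort dose contrasts are partly non-randomised, while alum contrasts within a dose are randomised throughout.

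If the separate SAP already specifies this, cite it in 6.4.3 instead.

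The cost is a few sentences. The baseline samples are already scheduled and trial conduct does not change. There are two downsides to state openly. The change must be dated and labelled as made after immunogenicity data were seen, since Section 1.3 already reports them. And adjustment removes only drift that shows in the pre-dose titre, and would add bias if that drift did not carry through to the post-dose titre; keeping the rank-sum result alongside lets a reader see whether the two disagree.

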1. INTRODUCTION

Respiratory syncytial virus (RSV) causes upper and lower respiratory infections in children and adults of all ages, and leads to significant morbidity and mortality in pediatric, immunocompromised, and geriatric populations [1]. Worldwide, RSV is the leading cause of respiratory tract infections in children, infecting 50-70% of all children by age one and nearly all children by age two [2, 3]. About 2% of all children will require hospitalization for RSV. Infants born prematurely or those with congenital heart disease have a particularly high risk for severe disease, but more than half of hospitalized infants, have no identified risk factors. The peak age of hospitalization is between 2 and 3 months of age, but more than half of all hospitalizations in children under 5 years of age occur after 6 months [4-7].

Other risk factors include a family history or genetic predisposition to allergic inflammation and increase in IL-13 and IL-4 responses or a low level of maternally-transferred RSV-specific neutralizing activity [8]. Additionally, infants hospitalized for RSV are at greater risk for childhood wheezing and asthma. Adults with compromised immune systems and those ages 65 and older are also at increased risk of severe disease [9, 10].

Nearly all humans contract RSV by the age of three and then repeatedly throughout their lifetime [11, 12]. The economic impact of RSV in the United States (US) alone exceeds \$400 million per year [13, 14] and worldwide, annual RSV hospitalizations are estimated to number more than 3.4 million [15].

Currently, there is no licensed RSV vaccine. A single licensed antiviral therapy, Palivizumab (Synagis™), is currently available for prevention of RSV. Palivizumab is an anti-RSV fusion protein-specific monoclonal antibody (mAb) used as passive prophylaxis to reduce the frequency of severe RSV disease in premature infants, but is only recommended for infants born at 28 weeks of gestational age or less [16-20]. Target populations for an RSV vaccine include pregnant women, infants, young children, and the elderly. It is anticipated that age-specific vaccine strategies will be needed to generate effective immunity across a range of age groups [21].

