6.3.2. Power Calculations for Evaluation of Immunogenicity

Although immunogenicity is a secondary endpoint, it is of sufficient interest that we briefly present the power to detect a difference between immune responses before and after the first dose, and between two dose cohorts. Based on previous research[44], we expect the ELISA and neutralization results to be approximately normally distributed on the \log_{10} scale, with standard deviation approximately 0.2-0.5 \log_{10} . Using the conservative value of 0.5 \log_{10} for the true standard deviation, we will have good power (90% or better) to detect a difference in the magnitude of the immune response of approximately .45 \log_{10} with 15 per group. With 30 per group, we will be able to detect a difference in the average magnitude of approximately 0.3 \log_{10} .

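### The lead between-group immunogenicity test uses neither Day 0 titre nor dose, and no effect estimate is committed to; for alum this costs power and precision, not validity

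*Combined protocol and SAP*

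**What the plan says.** Section 6.4.3 names the test for the time points that it treats as primary for immunogenicity: "The primary comparisons at 2 and/or 4 weeks post first dose will be compared using Wilcoxon Rank Sum tests". The between-subject contrasts are "between dose cohorts and between those who receive Alum and those who do not". The same section adds that "regression models will also be explored that model post-dose immune response as a function of pre-dose immune response, dose, Alum (yes/no") and possibly demographic variables. It names no effect measure or confidence interval for a between-group difference. The analysis cohorts are to be "specified in the Statistical Analysis Plan (SAP"); the supplied text contains no separate SAP, and Section 6.4.3 refers to one for the cohorts only.

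The baseline is available. Section 1.4 plans baseline specimens, Section 4.2.3 requires research samples before each injection, and Appendix III lists Day 0 serum. Section 6.4.6 randomises alum against no alum 1:1 within each dose level. Section 4 sets the two-injection regimens with and without alum against each other at each dose level. Section 6.4.3 does not say whether its alum contrast is per dose (15 v 15) or pooled (45 v 45).

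**The concern.** The trial enrols adults with existing immunity: "Nearly all humans contract RSV by the age of three and then repeatedly throughout their lifetime" (Section 1). Day 0 neutralising titres should therefore be present and vary between subjects. If they predict the post-dose titre, part of the spread that the rank sum treats as noise can be explained by a covariate already collected. The plan names that covariate but leaves it out of its lead analysis, which matters with 15 per group.

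Dose raises a second point. If the alum contrast is pooled over three dose levels without accounting for dose, any dose response adds to the spread within both alum arms and weakens the test.

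Third, a rank sum p-value alone does not tell the reader how large the alum effect is or how precisely it is known, which is what a Phase I trial mainly needs to report.

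**Working it through.** **Inputs.** Section 6.3.2 assumes approximate log10 normality "with standard deviation approximately 0.2-0.5" log10, takes 0.5 as conservative, and uses a difference of 0.45 log10 with 15 per group. Section 6.3 gives 6 groups of 15. Assumed because the documents do not state them: two-sided 5% per test; pre/post correlation r of 0, 0.3, 0.5 or 0.7; equal pre- and post-dose SD.

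**The plan's own figure.** Section 6.3.2 says "we will have good power (90% or better) to detect a difference in the magnitude of the immune response" of about 0.45 log10 with 15 per group. This reproduces as a paired before/after t test with SD of the difference 0.5: power 89.9%. For two groups of 15, SE = 0.5 × √(2/15) = 0.183 and 0.45/0.183 = 2.46. The two-sample t test then has 66.3% power, and the Wilcoxon about 64.1% using its relative efficiency of 3/π.

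**Day 0 adjustment, 15 v 15.** Adjustment multiplies the SE by about √(1 − r²), less a small cost for one extra parameter. The factors are 1, 0.954, 0.866 and 0.714 for the four correlations. Simulated power for 0.45 log10 (20,000 replicates per setting):

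| SD | Rank sum, post-dose titre | Model with Day 0 titre, r = 0 / 0.3 / 0.5 / 0.7 |
|---|---|---|
| 0.5 | 62% | 64 / 69 / 77 / 90% |
| 0.4 | 81% | 83 / 86 / 92 / 98% |
| 0.35 | 90% | 92 / 94 / 97 / 99.6% |
| 0.3 | 97% | 97 / 98 / 99 / 100% |
| 0.2 | 100% | 100%, no gain |

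At SD 0.5 the gain is 2, 7, 15 and 28 points. With no true difference, the rank sum rejects in 4.4–4.7% and the model in 4.9–5.2%, so both are valid. With a pre-dose SD of 0.3 and post-dose SD of 0.5, the model gives 65 / 68 / 77 / 90%, so the equal-SD assumption matters little.

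**Precision.** The expected 95% CI half-width at SD 0.5 is 0.371 log10 unadjusted and 0.378 / 0.360 / 0.328 / 0.270 adjusted. Dividing by 0.371, the interval is 2% wider at r = 0 and 3, 12 and 27% narrower at 0.3, 0.5 and 0.7.

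**Pooling over dose, 45 v 45.** Assume dose means of 0, 0.2 and 0.4 log10. Their variance is (0.2² + 0 + 0.2²)/3 = 0.0267. The pooled test sees a spread of √(SD² + 0.0267), but dose is balanced between alum arms, so the difference varies only with SD. The effective critical value is 1.96 × √(SD² + 0.0267)/SD:

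- SD 0.5: 1.96 × 0.526/0.5 = 2.06, true-null rejection 3.9%
- SD 0.35: 1.96 × 0.386/0.35 = 2.16, rejection 3.1%
- SD 0.2: 1.96 × 0.258/0.2 = 2.53, rejection 1.1%

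Simulated rank sum rejection agrees at about 4, 3 and 1%; it is 5% if dose means are equal. For an alum effect of 0.30 log10 at SD 0.5, the pooled rank sum has 75% power, against 80 / 83 / 90 / 98% for the model with dose and Day 0 titre. At SD 0.35 it is 96% against 98–100%; at SD 0.2 all are near 100%.

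**Stratifying by dose.** With larger assumed dose steps of 0.3 log10 (SD 0.5, effect 0.30, 800 runs), stratifying the rank sum raises its power from 71 / 70 / 69 / 74% to 78 / 77 / 74 / 78%. The model gives 83 / 83 / 87 / 98%.

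**The case against.** The rank sum is a valid, robust test, the covariate regression is already in Section 6.4.3, and immunogenicity is a secondary endpoint in a Phase I trial. The gain depends on a correlation that the documents do not give, and it is small if that correlation is near 0 or the SD is low. All of this stands, and it limits the size of the point.

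The rank sum may also be the better test. The plan says "we expect the ELISA and neutralization results to be approximately normally distributed" on the log10 scale. With heavy tails (t on 3 df, SD 0.5), ranking post-dose titre gives 85% against 76 / 79 / 85 / 93% for the model; on 5 df it is 72% against 68 / 72 / 79 / 91%. This stands too, and is why the rank sum should be kept.

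The strongest objection is timing. Section 1.3 shows 95 subjects enrolled by August 2019 and neutralisation results already reported in an open-label trial. Replacing the lead analysis now would be a post-data switch, so the remedy has to be a disclosed addition.

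A reader might infer more than the documents support:

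- That the ranked variable is wide open between post-dose titre and change from Day 0, with a large swing in power. Section 6.4.3 uses the word magnitude for values both before and after a dose, so the level at a visit is the natural reading; one clarifying phrase is enough.
- That Section 6.3.2 promises 90% power for alum against no alum. It names before/after and between-dose-cohort comparisons, not alum.
- That interim reports will select a dose or the adjuvant. Section 6.4.5 lets them inform future trial-related decisions but bars any influence on early termination or later endpoint assessment.

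**Conclusion.** The point holds as one of efficiency and reporting. The lead between-group analysis leaves out a Day 0 titre that is already collected, does not account for dose, and commits to no estimate with a confidence interval. At the plan's conservative SD of 0.5, 15 v 15 and 0.45 log10, the cost against a Day 0-adjusted model runs from 2 points of power (r = 0) to 28 points (r = 0.7). At SD 0.35 it is 2 to about 10 points, and at SD 0.2 nil. Pooling alum over doses without accounting for dose makes the test conservative when dose means differ. These sizes rest on assumed correlations, assumed dose means and approximate log10 normality.

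It would be wrong to call the alum comparison biased: randomisation within dose protects it. For dose contrasts, Sections 4.3 and 6.4.6 openly describe groups opening in sequence until each has at least 10 subjects. A note that these contrasts are partly non-concurrent is a labelling matter; the documents give no drift from which to size a bias.

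**What to change.** For each primary time point after the first dose, commit to a linear regression of log10 post-dose neutralisation titre on log10 Day 0 titre, dose level (three levels) and alum. Report the alum effect as an adjusted geometric mean ratio with 95% CI in two ways: within each dose level, from the model with dose-by-alum terms, and pooled over doses, with dose in the model.

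Keep the planned Wilcoxon test with equal visibility. State that it ranks post-dose titre and, if alum is pooled, stratify it by dose. Describe dose contrasts as partly non-concurrent. Date the change and disclose that it was made after immunogenicity data had been reported.

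The cost is analysis wording only, with no new samples or visits. The drawbacks are that it is a post-data addition; that the model relies on approximate log10 normality and can lose to the rank sum with heavy tails; that it gains almost nothing if Day 0 titre hardly predicts the response; and that the pooled ratio assumes a similar alum effect at each dose, so the within-dose ratios must be shown with it.
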